3.5.3. Vital Signs Data

Blood pressure, pulse rate, respiratory rate and temperature will be taken at times detailed in the SoA given in the protocol. Baseline is defined as the last pre-dose measurement collected on Day 1. Change from baseline in supine systolic and diastolic blood pressure, pulse rate, temperature and respiratory rate will be determined.

3.5.4. ECG Results

Triplet 12-lead ECGs will be obtained at each assessment time indicated in the SoA given in the protocol. The average of the triplicate readings collected at each assessment time will be calculated for each ECG parameter. Baseline will be defined as the average of the triplicate pre-dose recordings on Day 1. Change from baseline in QT interval, heart rate, QTcF interval, PR interval, and QRS complex will be determined.

4. ANALYSIS SETS (POPULATIONS FOR ANALYSIS)

For purposes of analysis, the following analysis sets are defined:

Participant Analysis Set	Description
Enrolled/Randomly assigned to study intervention	"Enrolled" means a participant's, or his or her legally authorized representative's, agreement to participate in a clinical study following completion of the informed consent process and screening. A participant will be considered enrolled if the informed consent is not withdrawn prior to participating in any study activity after screening. Potential participants who are screened for the purpose of determining eligibility for the study, but do not participate in the study, are not considered enrolled, unless otherwise specified by the protocol.
PK Concentration Analysis Set	The PK concentration population for an analyte is defined as all participants assigned to investigational product and treated who have at least 1 concentration measured.

Participant Analysis Set	Description
Enrolled/Randomly assigned to study intervention	
"Enrolled" means a participant's, or his or her legally authorized representative's, agreement to participate in a clinical study following completion of the informed consent process and screening. A participant will be considered enrolled if the informed consent is not withdrawn prior to participating in any study activity after screening.
 
Potential participants who are screened for the purpose of determining eligibility for the study, but do not participate in the study, are not considered enrolled, unless otherwise specified by the protocol.

PK Parameter Analysis Set	
The PK parameter analysis population for an analyte is defined as all participants assigned to investigational product and treated who have at least 1 of the PK parameters of primary interest measured.

Safety Analysis Set	
All participants enrolled to study intervention and who take at least 1 dose of study intervention. Participants will be analyzed according to the product they actually received.

5. GENERAL METHODOLOGY AND CONVENTIONS

5.1. Hypotheses and Decision Rules

There is no statistical hypothesis testing planned for this study and no statistical decision rules will be applied.

5.2. General Methods

All data will be descriptively summarized.

Binary and categorical variables will be presented using summary statistics: number of observations and percentages.

Continuous variables will be presented using summary statistics: number of observations, arithmetic mean, standard deviation (SD), coefficient of variation (cv%), median, minimum, maximum, geometric mean and geometric cv%.

5.3. Methods to Manage Missing Data

5.3.1. Safety Data

For the analysis of safety endpoints, the sponsor data standard rules for imputation will be applied.

5.3.2. Pharmacokinetic Data

Concentrations Below the Limit of Quantification

In all PK data presentations (except listings), concentrations below the limit of quantification (BLQ) will be set to zero. (In listings, BLQ values will be reported as “<LLQ”, where LLQ will be replaced with the value for the lower limit of quantification (LLQ).)

Deviations, Missing Concentrations and Anomalous Values

In summary tables, plots of mean profiles and plots of median profiles, summary statistics will be calculated setting concentrations to missing if one of the following cases is true:

1. A concentration has been collected as ND (i.e., not done) or NS (i.e., no sample);
2. A deviation in sampling time is of sufficient concern or a concentration has been flagged anomalous by the pharmacokineticist.

Note that summary statistics will not be presented at a particular time point if more than 50% of the data are missing.

Pharmacokinetic Parameters

Actual PK sampling times will be used in the derivation of PK parameters.

If a PK parameter cannot be derived from a participant's concentration data, the parameter will be coded as NC (i.e., not calculated). (Note that NC values will not be generated beyond the day that a participant discontinues.)

In summary tables, statistics will be calculated by setting NC values to missing; and statistics will be presented for a particular dose with ≥ 3 evaluable measurements.

If an individual participant has a known biased estimate of a PK parameter (e.g., due to an unexpected event such as vomiting before all the compound is adequately absorbed in the body), this will be footnoted in summary tables and will not be included in the calculation of summary statistics.

6. ANALYSES AND SUMMARIES

6.1. Primary Endpoint(s)

The PK parameters detailed in [Section 3.1](#) will be listed and descriptively summarized for participants in the PK parameter analysis set (as defined in [Section 4](#)). Missing values will be handled as detailed in [Section 5.3.2](#). For each analyte (PF-07321332 plasma, **CC1** [REDACTED] and ritonavir plasma), the PK parameters will be summarized by study day. Each summary will include the set of summary statistics as specified in [Table 3](#).

Table 3. PK Parameters to be Summarized Descriptively

Parameter	Summary Statistics
C_{max} , AUC_{12} , C_{trough} , AUC_{tau} , AUC_{last} , C_{av} , R_{ac} , $R_{ac,Cmax}$, PTR, CL/F, V_z/F , CCI	N, arithmetic mean, median, cv%, SD, minimum, maximum, geometric mean and geometric cv%.
T_{max}	N, median, minimum, maximum.
$t_{1/2}$	N, arithmetic mean, median, SD, minimum, maximum.

For AUCs and C_{max} , box and whisker plots for individual participant parameters overlaid with geometric means will be plotted for each analyte. For C_{max} , box and whisker plots will be presented with both Days 1 and 10 on the same figure by analyte. C_{trough} over time will be plotted for each analyte. Supporting data from the estimation of $t_{1/2}$ will be listed by analyte where applicable.

For each analyte, the PK concentrations will be presented using participants in the PK concentration analysis set (as defined in [Section 4](#)) and will include:

- a listing of all concentrations sorted by participant ID and nominal time post-dose. The concentration listing will also include the actual times. Deviations from the nominal time will be given in a separate listing.
- a summary of concentrations and nominal time post-dose, where the set of statistics will include n, mean, median, SD, cv%, minimum, maximum and the number of concentrations above the LLQ.
- median concentration-time plots (on both linear and semi-log scales) against nominal time post-dose.
- mean concentration-time plots (on both linear and semi-log scales) against nominal time post-dose.
- individual concentration-time plots by dose (on both linear and semi-log scales) against actual time post-dose.

All figures (individual, mean, and median) will be presented with both Days 1 and 10 on the same figures. The scale used for the x-axis (time) of these plots will be decided on review of the data, and will depend on how long PF-07321332 and ritonavir concentrations are quantifiable.

The PK parameters of PF-07321332 and ritonavir on Day 1 and steady state obtained from this study will be used to compare with the corresponding PK parameters obtained from Studies C4671014 and C4671015 to evaluate the PK characteristics between Chinese and Western populations. These analyses and results will be presented separately from the clinical study report (eg, ethnic sensitivity analysis report or other appropriate documents).

PFIZER GENERAL BUSINESS

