2.1. Study Rationale

The purpose of the study is to investigate the PK, safety and tolerability of PF-07321332 following repeated oral doses in combination with a PK boosting agent ritonavir in Chinese healthy adults.

All comparisons to Western participants will be conducted outside this protocol and the CSR.

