9.3. Statistical Analyses

The SAP will be developed and finalized before any analyses are performed and will describe the analyses and procedures for accounting for missing, unused, and spurious data. This section is a summary of the planned statistical analyses of the primary and secondary endpoints.

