9.3.1. Statistical Methods for Pharmacokinetic data

The PK parameters of PF-07321332 and ritonavir will be listed and descriptively summarized by study day, respectively. For AUCs and C_{max} , box whisker plots for individual participant parameters overlaid with geometric means will be plotted for each analyte. For pre-dose concentration, plot of C_{trough} over time will be provided for each analyte. The PK parameters of PF-07321332 and ritonavir obtained in this study will be compared to the corresponding PK data from one or more global completed/ongoing studies which will be defined in SAP. The detailed statistical analysis will also be described in SAP. The comparative PK data for PF-07321332 and ritonavir may be from different studies depends on the specific study design. These results may be reported separately from the clinical study report (eg, ethnic sensitivity analysis report, brief document for submission, or other appropriate documents).

The concentrations of PF-07321332 and ritonavir will be listed and descriptively summarized by study day and nominal PK sampling times. For each analyte, individual participant and summary profiles (mean and median plots) of the plasma concentration time data will be plotted using actual and nominal sampling times, respectively. Additional specifications about the tables, listings, and figures will be outlined in the SAP.

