2. INTRODUCTION

The purpose of the study is to investigate the PK, safety and tolerability of PF-07321332 following repeated oral doses in combination with a PK boosting agent ritonavir in Chinese healthy adults. One (or more) suitable Western study(ies) will be selected for comparison between Western and Chinese population. This may involve comparison of Day 1 data and/or steady state data (generally reached by Day 2) with the data obtained from the Chinese Phase 1 study. The comparison results will be used to bridge global clinical data and support China registration of PF-07321332.

This statistical analysis plan (SAP) provides the detailed methodology for summary and statistical analyses of the data collected in Study C4671016. This document may modify the plans outlined in the protocol; however, any major modifications of the primary endpoint definition or its analysis will also be reflected in a protocol amendment.

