7. INTERIM ANALYSES

7.1. Introduction

No formal interim analysis will be conducted for this study. As this is an open-label study, the sponsor may conduct unblinded reviews of the data during the course of the study for the purpose of safety assessment, facilitating PK/PD modeling, and/or supporting clinical development.

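### Does the SAP need to specify the Chinese-versus-Western PK comparison in more detail?

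*SAP*

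**What the plan says.** Protocol 9.3.1 states that the PK parameters will be compared with data from one or more global studies to be named in the SAP. It continues: "The detailed statistical analysis will also be described in SAP". It also warns: "The comparative PK data for PF-07321332 and ritonavir may be from different studies depends on the specific study design". Protocol 9.3 adds: "The SAP will be developed and finalized before any analyses are performed".

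SAP 6.1 takes up the comparison in one short paragraph. The parameters of both analytes, on Day 1 and at steady state, "will be used to compare with the corresponding PK parameters obtained from Studies C4671014 and C4671015". Analyses and results go into a document separate from the clinical study report, such as an ethnic sensitivity report.

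On purpose and scope, SAP 2 says: "The comparison results will be used to bridge global clinical data and support China registration of PF-07321332". On occasions it says: "This may involve comparison of Day 1 data and/or steady state data (generally reached by Day 2". Protocol 2.1 says: "All comparisons to Western participants will be conducted outside this protocol and the CSR".

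**The concern.** The sentence in Protocol 9.3.1 that hands the detailed analysis to the SAP stands between two sentences about the comparison, so the natural reading is that it covers the comparison. The SAP then gives no measure (such as a ratio of geometric means), no interval, no list of parameters beyond the corresponding ones, and no assignment of study to analyte and occasion. SAP 5.2 and Table 3 list one-group statistics without intervals, and SAP 5.1 has no decision rule, so the rest of the readable SAP does not fill the gap. SAP 6.1 shows no redaction at this point.

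The stated use is bridging and registration, which makes a loose method look careless. The study is open-label, and SAP 7.1 says "the sponsor may conduct unblinded reviews of the data during the course of the study". If nothing fixed the comparison beforehand, the sponsor could in principle choose the more favourable comparator or parameter after seeing the data. Protocol 2.1, which puts all Western comparisons outside the protocol, also sits awkwardly beside Protocol 9.3.1, which assigns their method to this study's SAP.

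**Working it through.** **1. What is fixed and what is open.**

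| Element | Status in SAP 6.1 |
|---|---|
| Analytes | Fixed: PF-07321332 and ritonavir |
| Occasions | Fixed: Day 1 and steady state |
| Comparator studies | Fixed: C4671014 and C4671015, joined by *and* |
| Matching | Fixed: corresponding parameters |
| Place of reporting | Fixed: outside the clinical study report |
| Measure and interval | Not stated |
| Subset of parameters | Not stated |
| Study for each analyte and day | Not stated |

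The *and/or* in SAP 2 is introductory wording and allows both occasions. SAP 6.1 narrows it to both, so the two sections do not conflict.

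**2. Can the open items be filled from the plan's own outputs?** SAP Table 3 gives N, geometric mean and geometric CV for Cmax, AUC12 and AUCtau. SAP 6.1 singles out the AUCs and Cmax for box plots overlaid with geometric means, which points to the parameters and the scale. With the same three statistics from a comparator study, the ratio is GM(Chinese)/GM(Western). With a common log-scale SD s = sqrt(ln(1 + CV²)), the 90% interval is the ratio multiplied by exp(± t(0.95, n1+n2−2) × s × sqrt(1/n1 + 1/n2)).

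**3. How wide would it be?** Protocol 9.5 aims for about 12 evaluable participants, so n1 = 12. It gives no variability and no precision target, so there is no stated precision figure to reproduce. CV and n2 are assumptions, and the true ratio is set to 1.

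- CV 30%: s = sqrt(ln 1.09) = 0.2936.
  - n2 = 6: 1.746 × 0.2936 × 0.5000 = 0.256, giving 0.77 to 1.29.
  - n2 = 12: 1.717 × 0.2936 × 0.4082 = 0.206, giving 0.81 to 1.23.
  - n2 = 24: 1.691 × 0.2936 × 0.3536 = 0.176, giving 0.84 to 1.19.
- CV 20%, n2 = 24: 0.89 to 1.13.
- CV 40%, n2 = 6: 0.71 to 1.40.

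These widths come from sample size and variability. They do not depend on whether the SAP states the method.

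**4. Could a choice of comparator matter?** For Cmax and AUC, 2 analytes × 2 occasions × 2 parameters = 8 ratios. The number reaches 8 × 2 = 16 only if both studies supply every analyte, occasion and parameter. If they do, the Chinese mean cancels between the two ratios, and their log difference has SD s × sqrt(2/n2).

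At CV 30% and n2 = 12 that SD is 0.2936 × 0.4082 = 0.120. The two ratios then differ by a factor of at least exp(0.6745 × 0.120) = 1.08 half the time and at least exp(1.645 × 0.120) = 1.22 one time in ten. Over the corners used above these factors run from 1.04 and 1.10 (CV 20%, n2 = 24) to 1.16 and 1.44 (CV 40%, n2 = 6).

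This bears on the result only if the two studies overlap and one is then dropped. The documents do not describe the two designs, and the wording names both studies. If each study supplies a different analyte or occasion, the assignment follows from what was measured and nothing is left to choose.

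**The case for a change.** The strongest argument for a change is that the protocol made a specific promise and the SAP kept only half of it. Where results are reported is a different matter from where the method is set. Protocol 9.3.1 allows separate reporting and still gives the method to the SAP. A separate analysis plan may exist, but neither document cites one. The comparison has a stated regulatory use, sponsor review during the study is allowed, and one paragraph or one citation would close the point without adding a decision rule.

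Most of this stands as a description of the text: the cross-reference is not fully honoured, and a citation would be tidier. It does not show a wrong analysis. Protocol 9 lets the SAP modify what the protocol outlines and asks for an amendment only for major changes to primary endpoint definitions or their analyses. The Western comparison is not among the visible objectives or endpoints in Protocol 3 or SAP 2.1. Protocol 2.1, Protocol 9.3.1 and SAP 6.1 all point to another document as the place for this work. The worry about selective choice is limited because analytes, occasions and both studies are already fixed. An interval is good practice, but nothing in a study with no hypothesis and no decision rule requires a particular one.

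**Conclusion.** No change to the plan follows. SAP 6.1 leaves out the measure, the interval and the assignment of study to analyte and day, and Protocol 2.1 and 9.3.1 are loosely aligned. This is missing detail that a PK analyst would fill in the usual way, with geometric mean ratios and intervals for Cmax and AUC in the separate report. No rule in the plan gives a wrong result, and no listed endpoint, table or conclusion of this study is affected.

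For scale, a 90% interval for the ratio would span about 0.81 to 1.23 with 12 participants on each side at CV 30%, and from 0.89-1.13 to 0.71-1.40 over the assumed range. All of this is sampling error under assumed CVs and comparator sizes. Population is also confounded with study, which no interval covers. Writing the method into the SAP would alter neither fact. The factors of 1.08 and 1.22 apply only if both comparator studies supply the same analyte, occasion and parameter and one of them is left out, and the documents do not suggest that.

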6.2. Secondary Endpoint(s)

The details of safety analyses are described in Section 6.6.

The ritonavir plasma PK will be summarized and plotted the same as the primary endpoints described in [Section 6.1](#).

CC1

6.4. Subset Analyses

No subset analyses will be performed.

6.5. Baseline and Other Summaries and Analyses

6.5.1. Baseline Summaries

Demographic and baseline characteristics collected prior to the first dosing will be summarized following the sponsor reporting standard.

6.5.2. Study Conduct and Participant Disposition

Participant evaluation groups will show participant disposition. Frequency counts and percentages will be supplied for participant discontinuation(s). Data will be reported in accordance with the sponsor reporting standards.

6.5.3. Concomitant Medications and Nondrug Treatments

All concomitant medication(s) as well as non-drug treatment(s) will be reported according to current sponsor reporting standards.

6.6. Safety Summaries and Analyses

6.6.1. Adverse Events

Adverse events will be reported in accordance with the sponsor reporting standards.

6.6.2. Laboratory Data

Laboratory data will be listed and summarized in accordance with the sponsor reporting standards. Baseline is as defined in [Section 3.5.2](#).

6.6.3. Vital Signs

Absolute values and changes from baseline in blood pressure, pulse rate, temperature and respiratory rate will be summarized by time, according to sponsor reporting standards. Tables will be paged by parameter. Baseline is as defined in [Section 3.5.3](#).

Minimum and/or maximum absolute values and changes from baseline for vital signs endpoints (blood pressure and pulse rate) will also be summarized descriptively using categories as defined in [Appendix 1](#). Numbers and percentages of participants meeting the categorical criteria will be provided. All planned and unplanned post-dose time points will be counted in these categorical summaries.

6.6.4. Electrocardiograms

Absolute values and changes from baseline in QT, heart rate, QTcF, PR and QRS will be summarized by time using sponsor reporting standards. Tables will be paged by parameter. Baseline is as defined in [Section 3.5.4](#).

ECG endpoints and changes from baseline (QTcF, PR and QRS) will also be summarized descriptively by treatment using categories as defined in [Appendix 1](#). Numbers and percentages of participants meeting the categorical criteria will be provided. All planned and unplanned post-dose time points will be counted in these categorical summaries.

Listings of participants with any single post-dose value >500 msec will also be produced for QTcF.

7. INTERIM ANALYSES

7.1. Introduction

No formal interim analysis will be conducted for this study. As this is an open-label study, the sponsor may conduct unblinded reviews of the data during the course of the study for the purpose of safety assessment, facilitating PK/PD modeling, and/or supporting clinical development.

7.2. Interim Analyses and Summaries

Not applicable.

9. APPENDICES

Appendix 1. Categorical Classes for ECG and Vital Signs

Categories for QTcF

Absolute value of QTcF (msec)	>450 and \leq 480	>480 and \leq 500	>500
Increase from baseline in QTcF (msec)	>30 and \leq 60	>60	

Categories for PR and QRS

PR (ms)	max. \geq 300	
PR (ms) increase from baseline	baseline >200 and max. \geq 25% increase	baseline \leq 200 and max. \geq 50% increase
QRS (ms)	max. \geq 140	
QRS (ms) increase from baseline	\geq 50% increase	

Categories for Vital Signs

Systolic BP (mm Hg)	min. <90	
Systolic BP (mm Hg) change from baseline	max. decrease \geq 30	max. increase \geq 30
Diastolic BP (mm Hg)	min. <50	
Diastolic BP (mm Hg) change from baseline	max. decrease \geq 20	max. increase \geq 20
Seated pulse rate (bpm)	min. <40	max. >120

Appendix 2. List of Abbreviations

Abbreviation	Term
CCI	[REDACTED]
Ae _{tau} %	percent of dose excreted in urine as unchanged drug
AUC	area under the concentration-time curve
AUC ₁₂	AUC from time 0 to 12 hours
AUC _{last}	AUC from time 0 to T _{last}
AUC _{tau}	AUC from time 0 to time tau
BLQ	below the limit of quantitation
BP	blood pressure
C _{av}	average concentration
C _{max}	maximum observed concentration
C _{trough}	pre-dose concentration
CCI	[REDACTED]
CL/F	apparent clearance
CV	coefficient of variation
ECG	electrocardiogram
ID	identification
LLQ	lower limit of quantitation
NC	not calculated
ND	not done
NS	not sample
N/A	not applicable
PD	pharmacodynamic(s)
PK	pharmacokinetic(s)
PTR	peak-to-trough ratio
QTc	corrected QT
QTcF	corrected QT (Fridericia method)
R _{ac}	accumulation ratio for AUC _{tau}
R _{ac,Cmax}	accumulation ratio for C _{max}
SAP	statistical analysis plan
SD	standard deviation
SoA	schedule of activities
T _{1/2}	terminal elimination half life
T4	thyroxine
T _{max}	time for C _{max}
TSH	thyroid stimulating hormone
TEAE	treatment-emergent adverse event
V _{z/F}	apparent volume of distribution
